### Answer/Response:

Building on pilot work from our team exploring green space activity type, this study aims to focus specifically on older adults in Charlottesville and the surrounding areas. We aim to understand how green space activity type may influence belonging, loneliness and mood and how this may impact on willingness to return to JABA centers. Our research questions are as follows;

1. What types of green space activities have a beneficial impact on loneliness, belonging and mood in seniors who are JABA center members?
2. Does the inclusion of these activities encourage JABA service users to continue participation at their JABA centers?

To investigate these questions, we will utilize 2 study components. The first, titled 'activity sessions' refers to a participant group who will undergo a series of activities (on separate days) including walking, citizen science and planting in order to understand pre- and post-activity wellbeing. The second component, titled 'survey-only', refers to a different participant group who are remotely surveyed on their current wellbeing, experiences during COVID and barriers on returning to JABA. All participants will be JABA service users.

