**2. What are the statistical considerations for the protocol?**

The objectives section and the statistical section should correspond, and any objective for which analysis is unfeasible should be deleted. Also, the estimates and non-statistical assumptions of the statistical section should be supported by discussion in the background section.

The answer to this question should include:

- Study Design/Endpoints
- Recap of study objectives and endpoint definitions. An assessment of how study objectives will be assessed by identifying & defining which endpoints will be used to assess each component of the study objectives.
- The study design should include contingencies for early stopping, interim analyses, stratification factors (if applicable), and any characteristics to be incorporated in analyses.
- The power/precision of the study to address the major study endpoint(s), the assumptions involved in the determination of power/precision.
- If statistical hypothesis testing is included then specify the null and alternative hypotheses, the test statistic, and the type I and II error rates
- If precision of an estimate, then provide a definition for precision
- If other, then specify

Answer/Response:

This is a pilot study aimed at ascertaining impacts of outdoor activities on both wellbeing as well as understanding barriers to returning to JABA centers.

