**4. What is your plan for primary variable analysis?**

UVA Study Tracking: HSR210100

Version Date: 03-22-21

Page Number: 6 of 11

Include primary outcome(s)/predictor variable(s), statistical methods/models/tests to be employed, or descriptive summaries as appropriate. If not applicable, please provide explanation.

**Answer/Response:** We will use the following outcome measures across the study.

- Loneliness; measured by the UCLA Loneliness Scale, a 3-item scale that captures feelings of loneliness. (Activities and survey-only)
- Belonging; measured by the General Belonging Scale (GBS), a 12-item scale capturing social acceptance/inclusion and social rejection/exclusion. (Activities and survey-only)
- Acute Mood; pre and post measures of mood will be taken using the UWIST Mood Adjective Checklist (MACL), an acute measure of hedonic tone, stress and arousal. (Activities only)
- Restoration; Psychological restorative qualities of the setting measured by the Perceived Restorativeness Scale, a three point scale determining the restorative quality of activity spaces. (Activities only)
- Physical Activity; In addition to the arousal measure of the MACL, we will use the 10 point scale of the OMNI Perceived Exertion scale, to understand how physically exerted participants feel between activities. To understand baseline physical activity, we use the international physical activity questionnaire (IPAQ) to compare between studies (Activities and survey-only).
- Accelerometer; we will use accelerometers to measure participant movement throughout the activities to correlate with physical activity measures. (Activities only). Specifically, we will look to understand if increased movement, as measured by the accelerometer, correlates with increased feelings of exertion post-activity (across all three activities).

For measures taken in both the activities and survey-only, we will use an independent t-test using condition (activity or survey) to compare. For activities that use pre- and post-assessments, we will make change scores for each and use this in a one-way ANOVA, using activity type (three levels; walking, citizen science, planting) as the grouping variable.

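### Research question 1 asks which activity types affect loneliness and belonging, but no analysis by type is clearly specified for either outcome

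*Combined protocol and SAP*

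**What the plan says.** The first research question under Objectives/Hypothesis is: "What types of green space activities have a beneficial impact on loneliness, belonging and mood in seniors who are JABA center members". The factor of interest is the type of activity, and there are three outcomes.

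Statistical Considerations, question 4 (primary variable analysis), lists the outcomes with the component in which each is taken:

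- "Loneliness; measured by the UCLA Loneliness Scale, a 3-item scale that captures feelings of loneliness. (Activities and survey-only"
- belonging, on a 12-item scale, carries the same label for both components
- for mood, in the activity component only, "pre and post measures of mood will be taken using the UWIST Mood Adjective Checklist (MACL"

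Two analysis rules follow. The first is "For measures taken in both the activities and survey-only, we will use an independent t-test using condition (activity or survey) to compare". The second, which compares the activities with each other, is "For activities that use pre- and post-assessments, we will make change scores for each and use this in a one-way ANOVA"; its factor is the type of activity, with one level for each of the three.

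Question 5 (secondary variable analysis) is answered as not applicable. Study Procedures, question 1, has a survey before and a survey after the activity, under a protocol that is largely the same for all three sessions. It does not list the instruments in either survey. Study Design, question 1, says that each participant crosses over through all three activities.

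**The concern.** The only test expressly attached to loneliness and belonging compares activity participants with survey-only participants. Walking, citizen science and planting form one level of its factor, so it cannot show which of them helped. This is separate from whether the two groups are comparable: a perfectly matched survey group would leave the question about types just as open.

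The plan is also silent on when the two scales are taken in the activity group. An analyst who follows the expressly assigned rule would report by type for mood only, and a statement that one activity reduces loneliness more than another would have no specified analysis behind it. The silence affects data collection as well as analysis. If the scales are left out of the session surveys, the information by type cannot be recovered later.

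**Working it through.** **1. The plan's own sample size figure.** Human Participants, Subjects, gives 60 enrolled and about 10% attrition. 60 × (1 − 0.10) = 54, and 54 / 2 = 27 per group. This reproduces the stated figure. The point does not depend on it.

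**2. Each outcome in research question 1 against the stated rules.**

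| Outcome | Component | Pre/post stated for this measure? | Test clearly attached | Levels |
|---|---|---|---|---|
| Loneliness | both | no | t-test, activity or survey | 2 |
| Belonging | both | no | t-test, activity or survey | 2 |
| Mood | activity only | yes | ANOVA by activity type | 3 |

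One outcome of three has a clearly assigned analysis by type. Two do not, and question 5 adds nothing.

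**3. What the two-level test can show.** Suppose the activity group's value is a person's average over the three sessions. The activity-minus-survey contrast is then the mean of the three type effects. Take assumed effects in SD units, in the order walking, citizen science, planting:

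- (−0.3, −0.3, −0.3): mean −0.9 / 3 = −0.3; spread between types 0
- (−0.9, 0, 0): mean −0.3; spread 0.9
- (0, −0.9, 0): mean −0.3; spread 0.9
- (−0.6, −0.6, 0.3): mean −0.9 / 3 = −0.3; spread 0.9

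All four give the same contrast, although the differences between types run from 0 to 0.9 SD. If the value came from a single session instead, the test would set one activity against the survey and still would not compare the three.

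**4. Could the ANOVA rule cover these scales?** Its scope is worded by activity, not by instrument, and all three activities have a pre and a post survey. It would therefore cover loneliness and belonging if those surveys contain them. The text neither says that they do nor that they do not. On that reading a person has up to 2 × 3 = 6 values per scale, and the plan does not say which one enters the t-test.

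**5. Scale of a comparison by type (illustration only).** The documents give no alpha, power, effect size or SD. Assume two-sided alpha 0.05 and 80% power. With 27 per group, the t-test detects about 0.78 SD. A paired comparison of two activities in 27 people detects a standardised difference dz of about 0.56. In SD units this is dz × √(2(1 − ρ)), where ρ is the within-person correlation:

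- ρ = 0.3: 0.56 × √1.4 = 0.66
- ρ = 0.5: 0.56 × √1.0 = 0.56
- ρ = 0.7: 0.56 × √0.6 = 0.43

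The paired figures are for one pair of activities without multiplicity adjustment. The SD in each case is that of the quantity compared (a score, or a change score), so the paired figures and the t-test figure are not on a guaranteed common scale.

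**The case against.** The strongest reply is that the two analysis rules do not exclude each other. A measure can be compared between components by the t-test and also enter the ANOVA as a change score. The Objectives section says that the activity sessions serve to understand wellbeing before and after activity, and the Study Design section uses wellbeing for what the two components share. Where the plan means a baseline measure it says so, as for the physical activity questionnaire; loneliness and belonging carry no such label.

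This stands in part. A reader might infer that the two scales enter only the t-test, that the plan can say nothing about type for them, and that none of the roughly 27 × 3 = 81 person-sessions bears on the matter. The documents do not support that, because they never exclude the scales from the session surveys. The 81 also assumes that everyone retained attends all three sessions, which is not stated.

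The favourable reading, however, needs an assumption that the plan does not make. Mood is the only outcome described as acute and the only one given pre and post timing, and the survey contents are not listed.

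A reader might also apply the form's instruction that "any objective for which analysis is unfeasible should be deleted" and strike the objective. That goes too far: analysis by type is feasible if the scales are taken at each session. The fault is in the specification. Pilot status does not remove it, since the issue is which data are collected and how they are used, not power.

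**Conclusion.** The point holds as a gap between objective and analysis. For 2 of the 3 outcomes in research question 1, the only expressly assigned test has two levels and cannot separate the three activities, and no analysis by type is clearly specified. Whether the ANOVA was meant to cover them is undetermined, because the timing of the scales in the activity group is not stated. The non-identifiability in step 3 follows from the form of the test; the effect sizes there, and the alpha, power and correlations in step 5, are assumptions for illustration. The plan should be amended on either reading: on one, an analysis is missing; on the other, the timing and the value used in the t-test are missing.

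**What to change.** Preferred: state in Statistical Considerations, question 4, and in Study Procedures, question 1, that the 3-item loneliness scale and the 12-item belonging scale are in the pre- and post-activity survey at every session. Analyse their change by activity type with a repeated-measures or mixed model, because the same people do all three activities. Name the single time point that supplies the activity group's value for the t-test.

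The cost is at most 3 + 12 = 15 extra items per survey completion, or 15 × 6 = 90 item responses for a person who attends all three sessions; it is nothing if the scales are already in the surveys. These scales may change little within a session of up to 30 minutes, so a null result by type would need cautious reading.

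Alternative: limit the question about types to mood, and pose loneliness and belonging as change from before the first to after the last session. This costs the rewording of one research question and matching analysis text. The plan should then acknowledge that such a change is an uncontrolled before-after comparison. Neither option adds visits or participants.

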## Study Design: Biomedical

### 1. Will controls be used?

Answer/Response: Yes

► IF YES, explain the kind of controls to be used.

Answer/Response: There are two controls. First, during the activity sessions, participants will act as their own control, crossing over to take part in each activity. Second, we also will conduct a survey remotely in which participants will respond to questions regarding their current wellbeing. These will be compared to those of the participants who undergo the activity sessions.

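### The plan asks which activities benefit mood, but its only specified mood test compares the three activities with each other; no change within an activity is specified for reporting

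*Combined protocol and SAP*

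**What the plan says.** The Objectives/Hypothesis section gives two aims that involve mood. One is comparative: "We aim to understand how green space activity type may influence belonging, loneliness and mood". The other is research question 1: "What types of green space activities have a beneficial impact on loneliness, belonging and mood in seniors who are JABA center members". The same section says the activity sessions are run "in order to understand pre- and post-activity wellbeing". Statistical Considerations, item 2, describes the study this way: "This is a pilot study aimed at ascertaining impacts of outdoor activities on both wellbeing".

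Under item 4 (primary variable analysis), mood is measured before and after each activity with the UWIST checklist, "an acute measure of hedonic tone, stress and arousal. (Activities only"). Two analyses follow in that item:

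- "For measures taken in both the activities and survey-only, we will use an independent t-test". Mood is not measured in the survey-only group, so this test does not cover it.
- For pre/post measures, "we will make change scores for each and use this in a one-way ANOVA, using activity type" with three levels as the grouping variable.

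Item 5 (secondary variable analysis) is answered N/A. Study Design, item 1, says of the activity sessions that "participants will act as their own control, crossing over to take part in each activity".

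**The concern.** To say which activities benefit mood, one needs to know whether mood moved in each activity, and in which direction. The specified ANOVA addresses a different null hypothesis: that the mean change is the same in walking, citizen science and planting. It serves the comparative aim but not research question 1.

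A plausible and useful result for this pilot is that all three activities improve mood by about the same amount. Followed as written, the plan would then give a non-significant F and commit to nothing else that shows the improvement. That result could be reported as no effect.

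There is a second, separate weakness in the same sentence. A one-way ANOVA treats the three sessions as three independent groups, although each participant contributes to all three.

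**Working it through.** **Inputs from the documents.** 60 enrolled and about 10% attrition: 60 × 0.90 = 54, or 54 / 2 = 27 per group, which reproduces the plan's figure (Human Participants, item 2). There are three activities and three mood subscales (hedonic tone, stress, arousal). The plan states no alpha, power, effect size or SD for mood.

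**Assumptions not in the documents.** All 27 in the activity group complete all three sessions; two-sided alpha 0.05; normal change scores with SD 1; the same correlation ρ between any two sessions, taken as 0, 0.3 or 0.5.

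**Step 1: a benefit shared by all activities.** F is built from differences between activity means and from spread around those means. Adding a constant to every change score alters neither. As a check on one generated data set, adding 0.8 SD to all scores left F = 0.332 and p = 0.718 unchanged. The rejection rate under an equal benefit of any size is therefore the rate under no effect.

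**Step 2: what that rate is.** With n = 27 the test uses F(2, 78), critical value 3.11. The between-activity mean square is distributed as (1 − ρ)·χ²(2)/2. The within-activity mean square is [(1 + 2ρ)·χ²(26) + (1 − ρ)·χ²(52)]/78, with expectation [26(1 + 2ρ) + 52(1 − ρ)]/78 = 1. The ratio therefore centres near 1 − ρ instead of 1, and the test is conservative when ρ > 0.

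**Step 3: one activity differs by 0.5 SD, the other two show no change.** The sum of squared deviations of the means is 0.5² × 2/3 = 0.1667, so λ = 27 × 0.1667 = 4.5. Repeated-measures ANOVA uses F(2, 52) with noncentrality 4.5/(1 − ρ) = 4.5, 6.43 and 9.0.

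| | ρ = 0 | ρ = 0.3 | ρ = 0.5 |
|---|---|---|---|
| Equal change in all three, one-way rejects | 5% | 1.5% | 0.4% |
| Equal change in all three, repeated measures rejects | 5% | 5% | 5% |
| One activity differs by 0.5 SD, one-way | 45% | 40% | 37% |
| One activity differs by 0.5 SD, repeated measures | 44% | 59% | 75% |

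The second row shows that changing the ANOVA type alone leaves research question 1 unanswered. The last two rows concern only the separate repeated-measures issue.

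**Step 4: what within-activity reporting would give.** The 95% CI half-width for one activity's mean change is t(0.975, 26)/√27 = 2.056/5.196 = 0.40 SD. A one-sample t-test against zero has about 71% power for a change of 0.5 SD. For a pairwise difference the half-width is 2.056 × √(2(1 − ρ)/27) = 0.56, 0.47 and 0.40 SD at ρ = 0, 0.3 and 0.5.

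**Step 5: if only 20 complete all three sessions.** The single-activity half-width becomes 0.47 SD. Power in the step 3 scenario is 34%, 28% and 24% one-way, against 33%, 45% and 59% for repeated measures. The equal-change rates barely move.

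**The case against.** The strongest reply is that the question about types of activity is itself comparative. The Background presents walking as the default activity against which a cerebral and a physical activity are set, and Study Design names crossing over between activities as the control. On that reading the ANOVA is the controlled comparison, and a pre-post change with no control session is weaker evidence. This stands in part: the comparison belongs in the plan, and within-activity change should not be ranked above it. It does not remove the gap, because the wording about beneficial impact and about wellbeing before and after activity also asks for the change itself.

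A second reply is that the activity means would be shown anyway. They may be. A reader might infer that the plan rules out reporting within-activity change, but the documents do not support that. Change scores are to be made for each pre/post measure, and nothing forbids summarising them. The plan is silent.

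Nor should one infer that the direction of an effect would be lost. In the scenario with one activity differing by 0.5 SD, the differing activity's observed mean has the right sign in over 99.9% of significant results. Committing to report the means settles direction.

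Finally, this is a pilot with a sample set by feasibility. That limits how much weight any test can bear, but it favours estimates with intervals.

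**Conclusion.** The point holds as a gap in specification. For mood, the plan specifies one between-activity test, which does not respond to an improvement common to all three activities, and it specifies no within-activity change for reporting. Under the stated assumptions the test flags such an improvement about 5%, 1.5% or 0.4% of the time at ρ = 0, 0.3 or 0.5. The insensitivity itself is algebraic and does not depend on those assumptions. Reporting an equal improvement as no effect is a risk that the plan leaves open, not something it states will happen.

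Separately, the one-way ANOVA does not match the crossover design. A reader might infer that this inflates false positives. With positively correlated sessions it does the opposite and loses power (37% against 75% at ρ = 0.5 in the scenario above). The size of the loss depends on a correlation that the documents do not give.

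This should be fixed before analysis. It does not invalidate the data collection.

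**What to change.** In Statistical Considerations, item 4, for each of the three mood subscales:

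- (a) Report the mean pre-to-post change with 95% CI within each activity, to address research question 1, alongside the between-activity comparison and not ranked above it.
- (b) Replace the one-way ANOVA with a repeated-measures ANOVA, or a mixed model with participant as a random effect.
- (c) Report the three pairwise differences between activities with 95% CIs.

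Label the tests exploratory and state the count: 3 × 3 = 9 changes, 3 × 3 = 9 pairwise contrasts and 3 omnibus tests, 21 in all for mood. Describe the results as pre-post change, not as causal benefit. There is no session without an activity, and this fix does not remove that limit.

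Extend the same approach to loneliness and belonging only if the plan confirms that they are collected before and after each session. With one total score per scale there would then be 5 outcomes × (3 + 3 + 1) = 35.

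The cost is slightly more analysis and a longer list of exploratory estimates. No new mood data are needed, since Study Procedures already has a survey before and after each session. With about 27 participants the intervals are wide, so small changes will remain uncertain.

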## Statistical Considerations

### 1. Is stratification/randomization involved?

Answer/Response: No

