**Answer/Response:**

There are two components to this study, so we describe each separately. *Activity sessions*

There will be three activity sessions, the protocol for each is largely the same. For the walking and the citizen science sessions, participants will be transported (Jaunt bus) to a nature preserve to conduct this session. Alternatively, if participants wish to transport themselves, they are welcome to – this will be confirmed after obtaining consent. The planting session is held at the JABA center. Upon arrival at the given site, participants will be given their initial pre-activity survey to complete (pen and paper) and are given an accelerometer to wear throughout the study session. Following this, they will undertake their activity; this will include a short nature walk, a guided citizen science walk or a session planting and tending to greenery in raised beds. At the end of the sessions (up to 30 minutes), participants will complete the post-activity survey and remove their accelerometer. After payment (\$10 supermarket voucher per session), participation ends.

*Survey Only*

Participants are mailed a study information sheet and the the survey with a return envelope. They are asked to complete the survey and return it to the research team.

**1. If this protocol involves study treatment, explain how a subject will be transitioned from study treatment when they have completed their participation in the study.**

**Example:** If the subject will be taking an investigational drug, will they need to be put back on an approved drug when they have completed the study? If yes, explain how this will be accomplished and who will cover the cost. If the subject has a device implanted will it be removed? Again- who will cover the cost of the removal?

**Instructions:** Answer NA if this study does not involve a study treatment.

**Answer/Response:** N/A

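### Mood is analysed as raw change scores; adjusting the post-activity score for the session pre-score would tighten the activity contrasts without new data, but the planting contrasts need the change-score estimate beside it

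*Combined protocol and SAP*

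**What the plan says.** Statistical Considerations, question 4, names the UWIST Mood Adjective Checklist (MACL: hedonic tone, stress, arousal) as the measure for which "pre and post measures of mood will be taken using the UWIST Mood Adjective Checklist (MACL"). It is the only measure explicitly described as taken before and after. For such measures the plan is that "we will make change scores for each and use this in a one-way ANOVA". The factor in that analysis is the activity, with one level for each of the three sessions. No covariate is mentioned, and question 5 (secondary analysis) is answered as not applicable.

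The pre-score exists at every session. Study Procedures, under Activity sessions, says "There will be three activity sessions, the protocol for each is largely the same", and "Upon arrival at the given site, participants will be given their initial pre-activity survey to complete". Under Study Design, question 1, "participants will act as their own control, crossing over to take part in each activity".

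Two further facts limit the remedy. The question "Is stratification/randomization involved" (Statistical Considerations, question 1) is answered No, and no order scheme is described. Walking and citizen science take place at a nature preserve, while planting takes place at the JABA center.

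**The concern.** A change score gives the pre-score a fixed weight of 1. Once each participant is compared with themselves across activities, stable personal differences have already cancelled. What remains in the pre-score is session-to-session variation, and only part of it predicts the post-score. Subtracting all of it brings the rest in as noise. A regression weight estimated from the data uses only the predictive part.

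Precision matters here. About 27 participants are expected in the activity component, and the sample size rests on what can be recruited. The first research question asks which activities help mood, so the contrasts between activities are what the reader will look at. The loss is distinct from the independence problem in the same sentence of the plan: a repeated-measures ANOVA of change scores would have the right error term and the same loss of precision.

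**Working it through.** **Plan's own figure.** 60 × (1 − 0.10) = 54, and 54/2 = 27 per group. This reproduces the stated final sample. The plan gives no SD, correlation, alpha or power, so there is no precision figure to reproduce.

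**Inputs.** n = 27 participants × 3 sessions = 81 sessions, from the protocol. Assumed: equal pre and post SDs, within-person SD set to 1, and r = 0.3 to 0.7, with 0.9 as a check. Here r is the within-person, within-session pre/post correlation.

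**Variance of a contrast between two activities, within person.**
- Change score: 2 × 2(1 − r)/n
- Adjusted post score: 2 × (1 − r²)/n
- Ratio, adjusted to change: (1 − r²)/(2(1 − r)) = (1 + r)/2

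The slope must be estimated. After 27 participant and 2 activity degrees of freedom, 81 − 27 − 2 = 52 remain, so the penalty is about 1 + 1/(52 − 2) = 1.02.

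| r | (1 + r)/2 | × 1.02 | Simulated, 27 × 3 |
|---|---|---|---|
| 0.3 | 0.65 | 0.66 | 0.67 |
| 0.5 | 0.75 | 0.77 | 0.76 |
| 0.7 | 0.85 | 0.87 | 0.84 to 0.87 |
| 0.9 | 0.95 | 0.97 | 0.97 |

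The saving is therefore about 33% at r = 0.3, 24% at 0.5 and 14% at 0.7. In participants, a change-score analysis would need roughly 27/0.67 = 40 to 27/0.86 = 31 people to match the adjusted analysis on 27.

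**Equal SDs.** With post/pre SD ratio k, the ratio before the slope penalty is k²(1 − r²)/(1 + k² − 2kr). At r = 0.5:
- k = 1.3: 1.2675/1.39 = 0.91, a saving of 9%.
- k = 0.77: 0.4447/0.8229 = 0.54, a saving of 46%.

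**What a site shift does.** Suppose planting's scores are displaced by d both before and after the session, with no true activity effect. The change-score contrast has expectation d − d = 0. The adjusted contrast has expectation d − r·d = (1 − r)d. For d = 0.3:
- r = 0.3: 0.7 × 0.3 = 0.21
- r = 0.5: 0.5 × 0.3 = 0.15
- r = 0.7: 0.3 × 0.3 = 0.09

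The variance saved is 4(1 − r)/n − 2(1 − r²)/n = 2(1 − r)²/n. Setting this equal to the squared bias (1 − r)²d² gives a break-even shift d = √(2/27) = 0.27 within-person SD, whatever r is. At d = 0.3 the root mean squared errors in simulation, change versus adjusted, are 0.32 versus 0.34 (r = 0.3), 0.27 versus 0.29 (r = 0.5) and 0.21 versus 0.22 (r = 0.7). The advantage for planting is gone.

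In the same simulation, walking versus citizen science, which share the preserve, stayed within 0.005 SD of zero and kept the full saving.

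**The case against.** The strongest objection is that adjustment is not free in this design. Crossing over balances stable traits but not differences tied to the session. The pre-survey is completed after arrival at a site that depends on the activity, so site or travel could move it. This stands. It affects two of the three contrasts, and the documents cannot say whether such a shift exists or would last. A reader might infer that adjustment costs nothing; without randomisation that does not follow.

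A second objection concerns the comparator. A reader might infer that the planned test is noisier than one ignoring the pre-score, since at r = 0.3 the change score has 2(1 − 0.3) = 1.4 times the variance of the post score alone. That ratio describes the within-person contrast. In the planned one-way ANOVA, subtraction is what takes stable personal differences out of the error term. For example, if half the variance is between persons and r = 0.3, the total pre/post correlation is 0.5 + 0.5 × 0.3 = 0.65. The error variance is then 2(1 − 0.65) = 0.70 for change against 1.00 for post alone. The savings above are measured against a within-person change analysis, which is itself not what is planned.

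Third, mean change by activity answers the stated interest in wellbeing before and after a session, and this is a pilot with no power claim. That supports keeping change scores in the report and treating the point as an improvement. It does not remove the gain for comparing activities.

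Finally, a session-order term cannot be separated from activity if everyone follows the same order, and the protocol does not say whether order varies. This also stands and is reflected in the fix.

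**Conclusion.** The point holds as a cheap gain in precision. The plan as written is not invalid on this account: change scores are a legitimate summary, and they stay unbiased under a lasting site shift. Under equal SDs and r between 0.3 and 0.7, adjustment within person saves about 14 to 33% of contrast variance relative to change scores within person. At r = 0.9 it saves about 2 to 4%. The documents support neither r nor the equal-SD assumption, so the size is conditional.

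The gain is clean for walking versus citizen science only in the sense that they share a setting; activity is still not randomised. For the planting contrasts, a lasting shift above about 0.27 within-person SD would make the adjusted estimate the worse of the two. If a pre-score difference is only chance, adjustment is the better choice. The data alone will not settle which applies, so both estimates are needed there.

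**What to change.** Amend Statistical Considerations, question 4, before analysis.

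- For each MACL subscale, model the post-activity score in a mixed model with activity, the pre-score split into the participant's mean pre-score and the session's deviation from it, and a random participant effect. The split keeps differences between people from setting the weight used within people.
- Add session order only if order varies between participants, and state whether it does.
- For planting versus walking and planting versus citizen science, report the change-score estimate from the same within-person model beside the adjusted one. State in advance that an adjusted planting effect will not be claimed unless the change-score estimate supports it.
- Keep mean change by activity as a descriptive summary.

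The cost is a change of wording, two model degrees of freedom for the pre-score terms (more if order is included), and two extra estimates per subscale. No new data are needed. The same model also handles the three sessions per person, which a one-way ANOVA treats as independent.
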